- Today, 52.6% of new breast cancer cases occur in LMICs, and this is expected to grow to 70% by year 2020.ⁱ
- Two-thirds of the estimated 15,000,000 healthy-life years lost annually to breast cancer globally are from LMICs.ⁱⁱ
- 5-year survival is 40-60% in most LMICs as compared to 80-90% in High Income Countries (HICs).ⁱⁱⁱ

Lack of secondary prevention programs (population based screening) and enhanced treatment, are the two major differentiating factors for poorer breast cancer outcomes in LMICs. Tumors detected as a result of routine screening tend to be smaller, well differentiated and less likely to have regional lymph-node involvement, making treatment more effective and survival more likely.^{iv,v,vi} Smaller, earlier-stage tumors are amenable to better, less costly treatment options. The National Cancer Institute-supported Cancer Intervention and Surveillance and Modeling Network (CISNET) suggests that 28–65% (median 46%) of the observed decrease in BC mortality in USA can be attributed to screening, with the remainder attributed to adjuvant treatment.

1.2 Challenges with secondary prevention and early diagnosis of breast cancer in LMICs

In HICs, screening mammography and clinical breast exam (CBE) are the standards of care for BC screening and detection. Their efficacy, cost-effectiveness and effect on survival and mortality of BC have been well documented. However, availability and/or use of these modalities remain limited in LMICs.

Organized screening mammography is expensive, resource intensive, requires stringent quality assurance and a large, well-trained workforce of technicians and radiologists. The cost per year of life saved ranges between Int. \$3,468 and Int. \$16,000,^{vii viii} which is beyond the health spending capabilities of most LMICs. In terms of human resources, most LMICs simply do not have the radiology expertise capacity required for an effective mammographic screening program. India, for example, has 10% the number of radiologists of the U.S. but almost 4 times the population.^{ix} Clinically, mammograms are limited in women with dense breasts, which includes most women under 50 years of age. Culturally, in LMICs there are reservations about radiation based, sometimes painful mammogram tests.^x So even when mammography is available, it is often not utilized; Mexico's Ministry of Health reports that only 25% of the installed mammography units are in use.^{xi}

CBE. The World Health Organization and the Breast Health Global Initiative recognize CBE as a cost-effective measure to screen for BC in LMICs. In a study in Indonesia, CBE performed nearly as well as single-view mammography.^{xii} In an IARC-supported, cluster-

randomized controlled study in India, CBE has been shown to enable the detection of early-stage breast cancers.^{xiii} It is known however that the efficacy of CBE may be substantially lower (28-36%) in practice than is reported in clinical trials.^{xiv} Physical exams in community health practice are often less systematic and poorer quality than in many organized clinical trials.^{xv} So the true contribution of CBE to BC detection in healthy women, and to improved survival in BC patients, has come under question, resulting in recent calls to standardize and lower the subjectivity of CBE administration and reporting.^{xvi}

[figure not shown]
1.3 Health worker led “earlier detection”

The American Joint Committee on Cancer (AJCC) staging system indicates prognosis based on the size of the tumor at detection viz. stage of breast cancer. Identifying tumors at earlier stages (down-staging) can improve survival, assuming high-quality treatment is accessible. In the U.S., approximately 40 million women receive mammograms annually and roughly 232,000 new cases are identified; vast majority are detected at stage Tis and T1 with a 5-year survival of 100%. In the context of LMICs, where up to two-thirds of breast cancer cases present at late stages, systematic down-staging is required, such that majority of the cases would be identified at Stage II or earlier, where survival can be 93% or better (again, assuming treatment is available).

In LMICs, health workers, nurses and midwives represent the most affordable resource to bridge the accessibility gap due to the lack of secondary prevention programs like in HICs. What is needed is a low-cost, user-friendly technology that can be used by health workers with minimal training to administer standardized breast exams without any special infrastructure with the goal to down-stage breast cancer to at least Stage II. The low-cost technology must perform with better detection sensitivity than CBE (higher than 50%) and equally high specificity as CBE (94%) to accurately and effectively identify breast lumps in need of further diagnostic follow-up (diagnostic ultrasound, breast biopsy) without clogging the under-resourced infrastructure with false positives due to typical benign breast features (tissue variability, lumpiness and nodularity).

Contrast in elastic stiffness between normal and abnormal breast tissue has long been recognized (Harris '94). Breast cancers are known to be stiffer than normal breast tissues. Major medical device manufacturers are exploring different sensing mechanisms like Ultrasound Elastography and MRI, which use tissue stiffness to differentiate between malignant and non-malignant tissue.

[figure not shown]
1.4 Investigational Device

The Piezoelectric Finger (PEF, Fig1), invented by [name] and [name] at Drexel University is a novel, quantitative and low-cost elastic modulus (E) sensor that can measure tissue compression by simple electrical means. PEF's ability to apply a force and measure the displacement electrically, all within the finger, makes for an ideal “electronic palpation” sensor for *in vivo* breast tissue imaging. Detection of abnormal breast tissues (e.g., carcinoma in situ, intra-ductal carcinoma, lobular carcinoma, etc.), and benign growths (e.g., fibrocystic lesions, hyperplasia, and calcifications) can be achieved by performing an E scan. The size and depth of the abnormal breast tissue can also be calculated using adjacent fingers.

Figure 1

The current PEFS system (Product Name: Intelligent Breast Exam™ or iBE™, Fig. 2) consists of a hand-held compression probe containing a 4 x 4 array of PEFS, a custom built electronics board and a tablet. iBE communicates wirelessly with a mobile device to display the findings in real-time, to store and share the data digitally and to easily compare the results with past records. iBE has the potential to ‘optimize’ CBE by improving on its overall effectiveness to detect Stage I and IIa breast cancers with minimally trained health workers. iBE will also ‘standardize’ breast exams by assisting every health worker to administer and record breast exams objectively, consistently and with the ability to share the results easily using the mobile device app.

The device will be stored in [name] office at [name].

1.5 Feasibility Testing

1.5.1 Proof-of-Concept:

Early testing was performed using tissue models as part of the development of the proof-of-concept device. This testing included characterization of the device, establishing its ability to distinguish smooth and rough surface characteristics of benign and malignant tumors, and determining its depth limit *ex vivo* and *in vivo*. I

1.5.2 Ex-Vivo Tissue Testing:

We conducted testing on 71 *ex vivo* breast tissue samples under an IRB-approved protocol and compared PEF results with the pathology reports. Of the 71 cases, there were 33 cases of invasive cancer (32 cases of invasive ductal carcinoma and 1 case of invasive lobular carcinoma), 9 cases of ductal carcinoma in situ (DCIS), and 19 cases of benign conditions including fibrocystic, hyperplasia, calcifications, fibroadenoma, papilloma, and glandular tissues. The E values at the malignancies were 3-5 times those of areas of the normal breast tissues regardless of patients' ages.

1.6 Clinical Data to Date

In Vivo Testing: Forty *in vivo* evaluations of the 1x4 PEF-compression probe were conducted by [name] at his Hahnemann Hospital outpatient office under an IRB-approved protocol. These evaluations were performed for device development, not clinical utility. The probe was tested with various pushing depth, i.e., at 2 mm, 4 mm, or 6 mm pushing depths to assess the effect of different pushing depth on the measured elastic modulus map. The results showed that different pushing depths did not alter the tissue elastic map, in terms of the lesion location and size. The PEF measurements were compared to patients' mammography reports. All tests were blinded.

A total of 40 patients were enrolled and 46 lesions were confirmed by imaging or pathology. PEF reported 55 lesions, with 9 false positives and 2 true positives not originally found on imaging or palpation. The overall sensitivity of the PEF test was 40/46 or 87%. In women 40 years or younger the overall sensitivity was 19/19 or 100%. In women who had a lesion visible on mammography, PEF had a sensitivity of 83% (24/29). Of these, in women aged 40 or younger, PEF identified all 7 mammographically visible lesions, including 2 malignant lesions. When compared with ultrasound, PEF correctly identified 87% (34/39) in this group. Of these, in women aged 40 or younger, PEF identified 100% (19/19) of all ultrasound visible lesions.

UPenn Clinical Pilot Study

A total of 44 patients were enrolled in this prospective signal processing/algorithm development trial. Patients presenting to the Pennsylvania Hospital Women's Imaging Center for breast diagnostic services including ultrasound and/or diagnostic mammogram and/or needle biopsy were recruited for an iBE exam prior to biopsy. The final production prototype device was used for all studies.

The demographic result of the patient population is 59% Caucasian 34% African Americans, 2% Asian, and 4.5% unknown with an average age of 41 with one male having participated in the study. The patient population is comprised of those who needed breast diagnostic services of the 44 patients 50% were determined to be BIRADs 2, and the other 50% were BIRADs 3 or 4, zero patients were categorized BIRADs 1 or 5. 17 subjects of underwent a biopsy.

1.7 Risk/Benefits

The piezoelectric finger (PEF) is a battery powered, electrically insulated device and poses very little risk of electric shock to subjects. The maximum voltage is 5V and the maximum current is 1 mA, both of which are safe to humans. The PEF presses gently on the breast causing negligible discomfort, similar to an ultrasound exam. The subject may feel the contact of the polycarbonate holder without discomfort, and once the polycarbonate holder is in position, the PEFS will compress a maximum of 35 microns, which the subject will not be able to feel. In conclusion, PEFS will pose minimal risk to subjects with negligible discomfort.

This study will provide no direct benefit to subjects and there may or may not be any direct benefit to society. In the future, possible benefits to others include the ability for patients, for whom mammography is less effective or not available, to be screened for cancer.

2 Study Objectives

The company that has licensed the technology has received funding to develop a low-cost, reliable, and commercially viable device for screening individuals who don't have access to the benefits of mammographic screening. This device is called the iBE (see Section 1.2).

The goal of this research project is to measure the accuracy of the iBE device for detection of clinically relevant findings in the breast. This study would establish a validated sensitivity and specificity for breast lesion detection using the results of current mammography based breast screening. These results are needed in preparation for an international trial of the device in Low-Middle Income Countries. This research project will have no impact on clinical decision making.

3 Study Design

3.1 General Design

Determination of the accuracy of iBE for the detection of clinically relevant breast lesions will be performed by means of a prospective study. Subjects may participate during a previously scheduled visit to the women's imaging center. All women presenting to the imaging center, including screening, diagnostic or interventional procedures, will be eligible for participation. A subset of patients will undergo dual examinations by different trained individuals with the results compared for inter-rater reliability.

The estimated date for the investigators to complete this study (complete primary analyses) is approximately 2 years from study activation.

3.2 Study Endpoints

- To determine the sensitivity and specificity of iBE exams for the detection of clinically relevant breast lesions (defined as BIRADS 3-5 on imaging, and/or malignant on biopsy).
- To determine inter-rater reliability in the iBE production prototype.

4 Subject Selection

4.1 Inclusion Criteria

- 18 years of age and older
- Women and men with symptomatic breast lump (either by palpation or imaging) OR
- Asymptomatic women presenting to the imaging center for a screening mammogram.
- Signed Informed Consent

4.2 Exclusion Criteria

- Patients under 18 years of age
- Patients who previously participated in this study and are returning to the Women's Imaging Center for follow-up diagnostic tests

4.3 Subject Recruitment and Screening

Subjects will be offered participation in the study during their visit to the Women’s Imaging Center by the PIs, [name], [name], and/or their designee. This study may recruit up to 1000 subjects. Patient’s will be eligible for study participation if they have a scheduled visit for the Women’s Imaging Center and have not previously participated in this study. The reason for the patient’s visit, screening or diagnostic, will not affect their eligibility. Diagnostic visits are included as it is necessary to ensure the accuracy of the iBE device’s ability to detect BIRADs 3-5. The iBE device was created to use as a screening tool to detect clinically relevant breast lesions, defined here as BIRADs 3-5, with the purpose of giving patients proper follow-up recommendations without causing unnecessary anxiety of avoidable diagnostic tests.

5 Study Procedures

Participants will be recruited from the Women’s Imaging Center who are scheduled to undergo screening or diagnostic imaging including biopsies. Subjects will have the study explained to them and given the consent form to review early in their imaging center visit. After the subjects have had time to review the consent, the PI or designee will answer all questions. If she/he agrees and signs the consent form, they will receive a signed copy to take home with them. All subjects must meet the inclusion and exclusion criteria. Consent will be obtained prior to any study-related activities.

The iBE evaluation will be performed by a trained individual who is blinded to the outcome of the radiology studies at the time the iBE is performed. The trained individual will be a healthcare worker with minimum education (or equivalence) to a licensed practical nurse (LPN) or an ultrasound tech. This is the target education level for the intended iBE operators. The selected healthcare worker will be trained by [name], MD to administer the iBE and clinical breast exams. The trainee will follow [name] during clinic hours for 1-2 days and trained for clinical breast exams, similar training to a medical student. The iBE training will mostly be software and instrument training by the leading iBE user in the United States, [name]. A minimum of two healthcare workers will be trained.

[figure not shown]
Subjects will be scanned with the iBE device administered by the trained individual while in a supine position without breast immobilization similar to ultrasound testing. A bilateral iBE exam will be performed on the entire breast as well as a bilateral Clinical Breast Exam (CBE) the findings will be documented on the case report forms and the device tablet concurrently.

If the patient is selected to participate in the inter-rater reliability portion of the study, the subject will undergo both the iBE and the clinical breast exams twice performed by two different separately trained individuals sequentially during the same visit. The trained individuals will have their own case report forms and tablets that integrate to the iBE to prevent results sharing and bias. The selection for the inter-rater reliability portion of the study will be decided by the day of the week. The second trained individual will be present one a day week and that day all the patients will be asked to participate in the dual exam inter-rater reliability portion of the study.

These data are recorded and processed by an automated software algorithm and the results are displayed topographically on a “breast-map” with red areas showing positive findings and green areas showing negative findings. All the recorded data are collected on the tablet without HIPAA identifying variables. The tablet will assign a four digit subject number incrementally increasing for each subject prior to the iBE scan and this number will be recorded on the case report form. Results of the test will be reported to the patient as well as the radiology technologist and radiologist. The iBE evaluation may add between 10 and 30 minutes to the clinic visit. The iBE evaluation will be done prior to the patient’s original scheduled imaging visit. After the completion of the imaging visit the radiologist will evaluate the images and the iBE report. If there are areas identified on the iBE that are not resolved by the scheduled mammogram an ultrasound will be performed in the area of concern (if not already scheduled).

The current pathway of breast lesion detection can be modified in this protocol in order to ascertain the accuracy of the iBE device illustrated in Scheme 1 below. The current pathway of breast lesion screening and detection begins with a screening mammogram or a diagnostic mammogram/ultrasound. If nothing is detected by mammogram or ultrasound then the pathway is complete and a follow-up recommendation is given. However, if something suspicious is detected by the initial mammogram then additional imaging is requested such as an ultrasound. If the additional ultrasound reveals something suspicious a biopsy maybe recommended for confirmation or if a benign finding is revealed a follow-up recommendation is be given. The addition of iBE screening will only modify the current pathway if the iBE exam returns a positive result when the initial mammogram provides a negative result. If this occurs a study provided ultrasound will be recommended and the ultrasound’s results will be used to verify the iBE positive result. If the ultrasound invalidates the iBE positive result, it will be deemed a false positive and the diagnostic tests are complete. However, if the ultrasound confirms the iBE’s result [name] and the radiologist will discuss if further diagnostic intervention (i.e. biopsy) is required. Data on the final disposition of the imaging, any biopsies and any follow up imaging to 18 months after participation will be recorded in the database.

Scheme 1: Current Algorithm with Integrated Study Pathway

Quantitative Data

Quantitative data from the test will be documented and analyzed for accuracy metrics.

The iBE device collects only compression measurements and stores these data on the mobile device. Compression data are recorded for our records and a copy is available to UELS via Dropbox, which is backed up online and offsite.

We know the data are captured accurately because a unique file gets created at the end of every scan in a specific folder inside the DELL tablet. The app gives the user a notification that the data were saved properly to the tablet at the end of each scan.

The data sent to the UELS database are identical to those on the tablet, as they are synced between the folder inside the tablet and Dropbox. This ensures that an exact copy of the files created at the site are sent to UELS. These files use a unique ID entered by the user and have no identifiable patient information.

No identifiable data are collected or stored by the iBE software. iBE data are stored at UELS on an encrypted database. All data that are transmitted are de-identified and sent directly to the database from the device. Each study performed on the device has a unique number. The unique

study numbers are entered into the database at Penn and associated with a subject number. The results of the clinical breast exam are recorded on the touch screen in a similar heat map fashion.

Other data associated with each subject number includes age, bra size, BMI, and breast lesion location. In symptomatic individuals, imaging results, final diagnosis, type of lesion, imaging and pathology data will be collected on a separate CRF and entered in the Penn database.

The data listed above as well as identifiable demographic data will be entered into a REDCap database that is only accessible to the research team. The original signed consent documents and CRFs are kept in a locked office at [name].

6 Statistical Plan-[name]'s expertise

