6.1 Sample Size Determination

Based on a study of BIRADS grading of a mammography registry, 80% of all screening mammograms are BIRADS 1 and 2. The incidence of malignancy should be 1-2% of all screening mammograms. The screening center performs 11,000 screening mammograms a year plus over 3000 biopsies. About 600 breast cancers are diagnosed yearly. Since symptomatic individuals scheduled to undergo diagnostic imaging or biopsy are eligible to participate this will enrich the population categorized to BIRADS 3-5. Using a sample size of 1000 subjects provides 80% power.

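### The iBE operator is masked only to radiology results, while the sample is enriched with known-lesion subjects whose visit type, symptoms and lump site are not masked, so pooled sensitivity can be biased relative to screening use

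*Combined protocol and SAP*

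**What the plan says.** On masking, section 5 (Study Procedures) says: "The iBE evaluation will be performed by a trained individual who is blinded to the outcome of the radiology studies at the time". No other masking of the operator to subject information is stated. The separate forms and tablets in section 5 serve only to keep the two raters in the reliability subset apart.

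On who is enrolled, section 4.1 admits "Women and men with symptomatic breast lump (either by palpation or imaging) OR" asymptomatic women attending for screening. Section 5 recruits people "scheduled to undergo screening or diagnostic imaging including biopsies". Section 6.1 gives the purpose: "Since symptomatic individuals scheduled to undergo diagnostic imaging or biopsy are eligible to participate this will enrich the population categorized to BIRADS 3-5".

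On intended use, section 4.3 says: "The iBE device was created to use as a screening tool".

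On the exam, section 5 says: "A bilateral iBE exam will be performed on the entire breast as well as a bilateral Clinical Breast Exam (CBE". No order is given for the two exams. For the device readings: "These data are recorded and processed by an automated software algorithm". The iBE exam precedes the imaging scheduled for that visit.

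On recorded data, section 5 says: "Other data associated with each subject number includes age, bra size, BMI, and breast lesion location". It does not say who records the location, when, or from what source.

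On analysis, section 6.2 counts a true positive only when breast and quadrant agree with the reference finding. It pools all subjects and names CBE as a primary comparison.

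**The concern.** For a woman attending for screening, masking to radiology results is effective, because her mammogram comes after the iBE exam. The enrichment subjects differ. Someone with a palpable lump may know its side and place and can mention it. In the pathway that section 5 describes, biopsy follows suspicious imaging, so a biopsy visit is itself a sign of likely reference-positive status.

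These subjects are included precisely to supply reference positives, so they weigh heavily in the sensitivity estimate. An operator who knows where the lesion lies may apply the probe there with more care, and a true positive is scored by location. The study is meant to give validated accuracy figures ahead of an international trial of the device (section 2). What is at stake is whether the sensitivity carried forward describes a screening exam or a partly cued one.

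**Working it through.** This is a question of design and text. The plan gives no figure for it to reproduce.

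**Step 1. What the operator could know before the iBE exam, by type of subject.**

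| Subject | Information that exists before the exam | Covered by the stated masking? |
|---|---|---|
| Asymptomatic screening | No imaging yet at this visit | Yes |
| Lesion known only from earlier imaging | Side and site in the earlier report; possibly known to the subject | Only if the radiology studies in section 5 include earlier ones, which the text does not say; what the subject says is not covered |
| Palpable or self-reported lump | Side and place, known to the subject | No |
| Biopsy visit | The visit type implies an earlier suspicious finding | Visit type is not masked |

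The clear gap is in the last two rows. The second row is ambiguous.

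**Step 2. Whether that knowledge can reach the result.** Section 1.4 describes a hand-held probe with findings shown in real time. The algorithm standardises the reading of the data. It does not standardise contact, dwell time or repeat passes. CBE has no automated step at all. Section 5 trains the same worker in both exams, so if CBE came first, palpation could also guide the probe.

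**Step 3. How it enters the estimate.** Let w be the share of reference positives who are known-lesion subjects, S_scr the sensitivity in screening subjects, and S_aware and S_unaware the sensitivity in known-lesion subjects with and without operator knowledge. If the operator is aware in all known-lesion subjects:

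- pooled sensitivity = (1 − w) × S_scr + w × S_aware
- part due to awareness = w × (S_aware − S_unaware)
- part due to a different mix of lesions = w × (S_unaware − S_scr)

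The documents give none of w, S_scr, S_aware or S_unaware, so neither part can be calculated. The awareness part is positive whenever knowing the site helps the operator find the lesion. That is the likely direction under a location-matched endpoint, but it is a judgement.

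**Step 4. What the planned analysis could show.** With one pooled table, neither part is visible. Reporting by symptomatic or visit status would give an estimate of S_scr. Separating the awareness part also needs a record of what the operator knew, and the plan does not collect one.

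**The case against.** The protocol is silent on these points; it does not say that the operator is told anything. A scan confined to a known site would depart from the bilateral whole-breast exam in section 5, and the positive or negative call comes from software. The phrase about radiology studies may already include prior imaging. Lesion location may be recorded only after the scan. Section 2 states the objective as accuracy for clinically relevant findings, and symptomatic subjects are included openly and for a stated reason.

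Much of this stands, and it rules out several stronger readings that a reader might infer:

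- That sensitivity is biased upward as a matter of fact. The documents support only that it can be, most likely in that direction.
- That masking breaks down for every enrichment subject. For lesions known only from imaging, the text may already cover the site.
- That the effect cannot be dealt with afterwards. Section 5 provides a separate form for symptomatic individuals, so a screening-only estimate should be obtainable, though operator awareness would remain unmeasured.
- That the recorded lesion location reaches the operator. Nothing says so.
- That the size can be read from the protocol's figures. The 87% (40/46) in section 1.6 is a per-lesion result from an earlier 1x4 probe used for device development. The 0.95 in section 6.2 is the preliminary sensitivity. Neither is labelled as an unaware or aware value. The volumes in section 6.1 give 3000/(11,000 + 3000) = 21%, but that leaves out non-biopsy diagnostic visits and is a share of visits, not of reference positives. A point estimate above about 0.90 would also not mean that the planned z-test is passed.

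What the objection does not remove is the gap itself. Whole-breast coverage does not fix how carefully each area is scanned, automation does nothing for CBE, and neither masks a palpable lump or a biopsy appointment.

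**Conclusion.** The point holds as a gap in masking that matters because of the enrichment. A site could follow the plan exactly and still have an operator who knows the likely status or site in the subjects who drive sensitivity. Pooled iBE sensitivity, and CBE sensitivity more so, can then be biased relative to screening use, most likely upward. No size should be quoted.

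The conclusion rests on three assumptions: that some known-lesion subjects will reveal their symptoms or site, or that visit type will be evident; that probe handling affects detection; and that the accuracy of interest is that of the screening tool in section 4.3. It should be corrected before enrolment, because what the operator knew has to be recorded at the time.

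**What to change.** **Section 5.** State that:

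- the operator is masked to reason for visit, symptoms, prior imaging, and lesion side and site;
- consent, history and lesion location are obtained by study staff other than the operator who already handle consent and data collection;
- subjects are asked not to mention symptoms or side until both exams are recorded;
- iBE is done and recorded before CBE;
- the operator records afterwards whether visit type or lesion site became known.

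**Section 6.2.** Report sensitivity and specificity separately for asymptomatic screening subjects and symptomatic or diagnostic subjects. Add a sensitivity analysis excluding subjects in whom the operator became unmasked.

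**Cost.** Protocol and case report form wording, plus a short script for contact with subjects. Section 5 assigns questions about consent to the investigator or a designee; if that designee is the operator, someone else must take over the step. Some unmasking will still occur. The screening-only sensitivity will be less precise, because it uses only the reference positives in that group.
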